We will assess social skills by administering the Social Skills Questionnaire (SSQ);⁵² and social functioning using the Adolescent Social Self-Efficacy Scale (ASSES).⁵³

Suicidality Assessment

The Columbia Suicide Severity Rating Scale (C-SSRS) will be used to screen for and assess suicidal ideation. Those that do not meet inclusion criteria for this assessment will not be enrolled in the study. Participants who do not meet this criteria but express interest in the study may be reengaged and reassessed following a 2-month period. The C-SSRS will be repeated at the *End of Study* (V3) Visit to screen for any changes in suicidal ideation over the course of the study. The C-SSRS may be re-administered during the intervention period, as needed, should there be any concerns for safety or increasing symptoms.

Intervention Embedded Assessments

Cognitive Biases. Participants in both the WASABI and active control arm will complete embedded assessments immediately before and after the 12-week intervention. Additionally, for participants assigned to WASABI, during the intervention and program use period, WASABI weekly collects performance data on two cognitive assessments that capture attention bias assessment, and an interpretation bias assessment. Participants assigned to

receive WASABI will also complete a weekly SPAI-B assessment. Performance on these assessments will be modeled longitudinally to examine if these measures can serve as potential moderators and mediators of treatment efficacy.

The primary outcome measures, including assessment adherence, dCBGT and IM engagement, EMA, SPAI-B and overall program completion rates, reported adverse effects, usability ratings and clinician burden, will be used to assess feasibility, acceptability and usability of WASABI.

Secondary outcomes include clinical ratings of anxiety and social anxiety symptoms (LSAS-CA), self-report inventories of social anxiety symptoms (SPAI), broad measures of anxiety (MASC-2), as well as measures that capture social skills (SSQ), and social functioning (ASSEs).

Description of Protocol Devices (Software Program)

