The active control program is designed to: 1) be a face-valid approach to remediation in anxiety disorders, to ensure that participants remain blind to group affiliation, and match the experimental treatment program in halo or expectation-based influence on performance in outcome measures; 2) match the experimental treatment program in overall dCBGT session intensity, time-spent attending, and overall engagement; and 3) provide a comparison group that matches the experimental treatment group on the aforementioned attributes, but without the adjunct to treatment component, WASABI.

To use the active control, a participant opens Google Meet, a HIPAA-compliant videoconferencing and instant messaging application on an Internet-connected iOS mobile device and goes to a general log-in screen. The participant then logs in using a study provided account). Participants assigned to the active control are expected to join 12, 1 hour-long dCBGT sessions using the Google Meet application. These will be scheduled and facilitated by the WASABI Clinician. To complete the BrainHQ embedded assessments, a participant opens a standard application (BrainHQ) on an Internet-connected iOS device and goes to a general log-in screen. The participant then logs into the experimental treatment program platform through the BrainHQ application (using a study provided username that contains no personally identifiable information).

Application Security

BrainHQ: All usage and progress data collected through the BrainHQ application is encrypted then transmitted to a central server. Data is encrypted in transit and at rest, and access is limited and audited. Data collected through the BrainHQ platform will not include geographic information. IP address data is stored only in memory and in request logs, and is used for technical support and troubleshooting, but not persisted with the participant's data. However, data as it relates to dates that assessments are completed is collected and stored. The EMA

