We hypothesize that the innovative features of WASABI will improve the quality of treatment delivery and facilitate the generalization of trained skills into real-world settings. The measures collected to determine the efficacy of the program for this trial are clinical ratings of anxiety and social anxiety symptoms (LSAS-CA), self-report inventories of social anxiety symptoms (SPAI), broad measures of anxiety (MASC-2), self-report inventories of social skills (SSQ), and self-report inventories of social functioning (ASSES). To test this hypothesis, we will use a linear mixed model approach. We will first compare treatment and active control groups in the ITT population to determine if any differences in baseline demographic, characterization, outcomes variables, or total program use time remain after the randomization process. Any such factors that show trend level significant differences ($p < 0.1$) will be noted and used as covariates in the linear mixed model analysis. The criterion for statistical significance is $p < 0.05$. Results with $p < 0.1$ will be described as trends.

Performance on the attention bias and interpretation bias assessments will be modeled longitudinally to examine if these measures can serve as potential moderators and mediators. To test if the attenuation of attention and interpretation biases mediates improvements in outcome measures, we will use repeated-measures linear mixed modeling to test in the active group the effects of WASABI on LSAS-CA, SPAI, SSQ and ASSES, and then model outcomes as a function of performance improvements on the attention bias and interpretation bias assessments.

Because we are interested in examining the ecological validity of WASABI, we will not restrict the analyses only to participants who adhered to all intervention requirements. Within-group effect sizes (Cohen's d) will be computed using the mean change scores (post-intervention minus baseline) and the change score SDs.

These measures will be analyzed to power the pivotal study proposed for Phase II. For the FDA, we will collect data documenting that WASABI meets its design requirements when used in the field by clinicians and patients, and that clinicians deem its risk/benefit ratio as acceptable and view it as adequate/appropriate for the target population.

Data Management

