Statistical Analysis Plan

WASABI: Wiring Adolescents with Social Anxiety Via Behavioral Interventions

Protocol Number: PSC-1016-19

NCT03990870

Document Date: July 8, 2019

(1) ANALYSIS POPULATIONS

There are three *a priori* defined analysis populations, including a primary analysis population (i), a secondary analysis population designed to compare effect sizes in populations with no missing data (ii) and a population who completed all training visits (iii)

- i. *Intent to Treat (ITT) population:* This is the *a priori* primary analysis population, defined as including all randomized participants who attended at least one group video call.
- ii. *Intent to Treat (ITT) Fully-Evaluable (FE) population:* This is a secondary analysis population, defined as including all members of the ITT population that complete a post-intervention visit. Note that a participant may complete a specific visit but have missing data for a test in which case the participant is in the overall FE population but does not contribute data to the FE population for that visit, e.g., the number of evaluable cases for a specific test on a specific visit may be smaller than the FE population for that visit because of missing data.
- iii. *Intent to Treat (ITT) Completers (C) population:* This is a secondary analysis population, defined as including all members of the ITT-FE population who complete all intervention sessions. Note that the C populations are strict subsets of the FE populations; a person who completes the target number of videocalls but does not complete the evaluation visit is not a member of the C population.

(2) STATISTICAL PLAN

Feasibility

The Phase I data analysis plan *a priori* defines a primary intent-to-treat (ITT) population, a set of secondary evaluation populations, a set of primary outcome measures, a set of secondary outcome measures, a set of potential mediators/moderators, a single primary evaluation time point, a criterion for statistical significance, and a statistical analysis methodology for secondary outcomes.

- The primary ITT population is defined as all participants who attend one dCBGT video call. Note that this includes all randomized participants except those who drop/withdraw post-randomization and pre-training.

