For feasibility, we relied on descriptive statistics. For preliminary efficacy, in smaller sample sizes like ours, there is a greater likelihood that there will be larger differences at baseline between groups simply due to sampling error. Groups were compared on all baseline measures using Mann-Whitney U tests (for ordinal and continuous variables) or Pearson chi-square/Fisher's exact test (for categorical variables). To test whether groups differed in change over time, data were analyzed via linear mixed-effects models. Mixed-effects models are ideal for the analysis of longitudinal data, due to the fact that it tolerates missing observations—assuming that it is missing at random (MAR). First, simple growth models (change from baseline to post) were conducted to examine change over time (for all participants). Because complete case analyses have been shown to provide biased estimates in the presence of missing data (Enders, 2010), data were then modeled using the intent-to-treat (ITT) framework, in which all randomized subjects are included in the analysis, and missing data were handled via Full Information Maximum Likelihood (FIML). This method for handling missing data is considered a gold standard approach, as it gives relatively unbiased estimates (Enders, 2010), and is the standard for the analysis of randomized trials. For all models, fixed effects of time, group, and group x time interaction were included; a random intercept of subject was used. Kenward-Roger degrees of freedom were used due to the small sample size; statistical significance was evaluated at a two-sided alpha of $p = 0.05$; however, null hypothesis testing was de-emphasized given the small sample size of the control group ($n = 8$). We emphasize the effect size (Cohen's d) instead. Although various estimates of effect size exist for LMM, we chose a simplified version, defined as:

$$\frac{(\Delta_{(dCBT+WASABI)} - \Delta_{(dCBT)})}{\sigma_{pre}}$$

Where Δ refers to slope (i.e., change from baseline to post-intervention) and σ_{pre} refers to the pooled baseline standard deviation. Thus, values of d refer to change in standard deviation units from baseline.

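### The exploratory bias-mediation analysis is worded as a test of WASABI's effects within one group, which cannot show mediation of WASABI's added effect over dCBGT, and the SAP specifies no mediator or mediation model

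*Protocol*

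**What the plan says.** **Protocol, Data Analysis.** Bias performance is to be modelled over time to see whether it "can serve as potential moderators and mediators". For mediation, the stated question is whether weakening of the two biases mediates improvement in the outcomes. The method has two steps: a repeated-measures mixed model "to test in the active group the effects of WASABI on LSAS-CA, SPAI, SSQ and ASSES", then outcomes as a function of bias improvement. No arm term, arm-to-bias step or indirect effect is described. The same section plans a second mediation analysis, by engagement with the intervention, if engagement correlates with outcome change.

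**Which group.** The term used in the mediation step is not defined. The efficacy paragraph of the same section labels the arms differently: "We will first compare treatment and active control groups in the ITT population".

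**What the arms share.** Both are asked to attend 12 weekly one-hour dCBGT sessions. Under Active Control Program, the control is meant to "provide a comparison group that matches the experimental treatment group on the aforementioned attributes, but without the adjunct to treatment component, WASABI".

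**Bias data.** Under Intervention Embedded Assessments: "Participants in both the WASABI and active control arm will complete embedded assessments immediately before and after the 12-week intervention". The weekly series is narrower: "for participants assigned to WASABI, during the intervention and program use period, WASABI weekly collects performance data on two cognitive assessments".

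**SAP, section (2).** The plan says it defines a priori "a set of potential mediators/moderators", but none is listed afterwards. On the comparative models it says: "For all models, fixed effects of time, group, and group x time interaction were included". No bias or engagement term appears.

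**The concern.** The control arm exists so that the difference between arms isolates WASABI. Change within the WASABI arm combines WASABI with dCBGT, the passage of time and regression to the mean. If bias change and outcome change are correlated in that arm, the correlation may reflect how dCBGT works. Because the first step is worded as the effects of WASABI, such a correlation could be reported as WASABI's mechanism.

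The SAP is where this would normally be settled. It promises mediators and supplies neither names nor a model, so an analyst has only the Protocol's wording to follow. What is at stake is a mislabelled mechanism in a feasibility trial, not a wrong efficacy result.

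**Working it through.** The documents give no figure for the mediation analysis, so there is nothing to reproduce. The argument is structural; the numbers only illustrate it.

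**1. What one arm can estimate.** Let A = 1 for dCBGT+WASABI and 0 for dCBGT, M the change in bias and Y the change in outcome.

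- Arm to bias: M = α + a·A + error
- Bias to outcome: Y = β + c·A + b·M + error
- Indirect effect of WASABI through bias: a × b

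In the WASABI arm A = 1 for everyone, so mean bias change estimates α + a, and the two parts cannot be separated. A mean change of 0.8 SD is equally consistent with α = 0.8, a = 0 (all dCBGT or time) and with α = 0, a = 0.8 (all WASABI). The slope b is estimable in one arm; a, and so a × b, is not.

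**2. Inputs for the illustration.** From the documents: 12 per arm (Protocol, General Study Design), a control group of 8 (SAP, section 2), two-sided 0.05 (SAP, section 2). Assumed: bivariate normal change scores with SD 1, the same mean shift on bias and outcome, within-arm correlation ρ of 0.3, 0.5 or 0.7. The decision rule is also assumed, because the Protocol states none.

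**3. One arm, n = 12, shift 0.8 SD.** Rule: outcome change p<0.05 and bias–outcome correlation p<0.05. The paired t-test alone has power 0.714, and a correlation must reach |r| of about 0.58.

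| | ρ = 0.3 | ρ = 0.5 | ρ = 0.7 |
|---|---|---|---|
| Pattern appears | 11% | 27% | 53% |
| Also requiring bias change p<0.05 | 8% | 20% | 44% |
| Shift 0.5 to 1.0 SD (first rule) | 5–14% | 12–34% | 25–67% |

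By step 1 these rates are the same whether dCBGT or WASABI caused the change. That follows by construction; it shows the logic and is not an error rate of the plan.

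**4. Two arms.** Rule: arm to bias p<0.05, and bias to outcome given arm p<0.05.

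| | ρ = 0.3 | ρ = 0.5 | ρ = 0.7 |
|---|---|---|---|
| 12 v 12, WASABI adds nothing | 1% | 3% | 5% |
| 12 v 12, WASABI causes all the change | 13% | 32% | 45% |
| 12 v 8, WASABI adds nothing | 1% | 3% | 4% |
| 12 v 8, WASABI causes all the change | 8% | 22% | 35% |

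**5. Precision of the two-arm indirect effect when a = 0.** Variance = ρ²·Va + Va·Vb, with Va = 1/n₁ + 1/n₀ and Vb = (1 − ρ²)/(n₁ + n₀ − 4).

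- 12 v 12, ρ = 0.5: Va = 0.1667, Vb = 0.75/20 = 0.0375. Variance = 0.0417 + 0.0063 = 0.0479, so SD = 0.22.
- 12 v 8, ρ = 0.5: Va = 0.2083, Vb = 0.75/16 = 0.0469. Variance = 0.0521 + 0.0098 = 0.0618, so SD = 0.25.

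For ρ = 0.3, 0.5 and 0.7, the simulated 95% ranges are about ±0.32, ±0.45 and ±0.59 at 12 v 12, and ±0.38, ±0.52 and ±0.67 at 12 v 8, in outcome change-score SD. If WASABI caused all of a 0.8 SD change, the true indirect effect would be 0.8 × ρ = 0.24, 0.40 and 0.56. Each lies inside the corresponding range.

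**The case against.** **The stated question is mediation of improvement, not of the difference between arms.** This stands. A within-arm association with improvement can be estimated and is worth describing. What cannot stand is presenting it as an effect or mechanism of WASABI.

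**A reader might infer that the documents fix a one-arm analysis.** They do not quite. The group is undefined, and the efficacy paragraph calls the WASABI arm the treatment group. The WASABI arm is the natural reading because the comparator is called the active control and receives no WASABI, but it is an inference. Nor does the SAP adopt a one-arm model: a model with a group term cannot be fitted to one arm. The SAP neither carries the Protocol's analysis forward nor replaces it.

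**A reader might infer that mediators are named nowhere.** The Protocol names attention bias, interpretation bias and engagement. Only the SAP is silent.

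**A reader might take the one-arm percentages as the plan's false-positive rate.** They rest wholly on assumed effects, correlations and a decision rule. With other assumptions (0.5 SD bias change, a further 0.8 SD direct outcome change) the first rule gives about 12%, 34% and 74%.

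**The two-arm analysis is weak.** True. It detects a wholly WASABI-caused effect in 8% to 45% of simulated trials. That argues for an interval and a hypothesis-generating label. It does not make a one-arm association informative about WASABI.

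**Conclusion.** The concern holds in a limited form, and its severity is minor. If the mediation step is read as the WASABI arm alone, its result describes that arm and cannot show that bias change mediates WASABI's effect over dCBGT. This follows from the design and needs no numerical assumption. Separately, the SAP announces mediators and moderators, lists none and models none.

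A stronger reading, that this damages the trial's main results, is not supported. The primary outcomes are feasibility measures analysed descriptively. The efficacy comparison is the SAP's group-by-time model, which does contrast the arms. The Protocol concedes low power for the augmentation effect and calls the mediators only potential. Nothing links the mediation result to the Phase II sample size. The risk is a mechanism credited to WASABI that may belong to dCBGT.

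**What to change.** In SAP section (2):

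1. List attention bias and interpretation bias as candidate mediators. Using the pre/post scores planned in both arms, model arm to bias change, and bias change to outcome change adjusted for arm. Report the indirect effect with an interval, as hypothesis-generating.
2. List engagement too, since the Protocol plans it. Include an arm term for session attendance, which exists in both arms. Treat group-chat engagement as within-arm description only, because the control arm is not asked to use the chat (Protocol, Application Security).
3. Keep the one-arm and weekly bias analyses as within-arm associations. Do not label them the effect or mechanism of WASABI.

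**Cost.** This is wording only; no new data are needed. The drawbacks should be stated with it:

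- The indirect effect will be very imprecise at 12 v 12 or 12 v 8.
- The bias-to-outcome path is not randomised, even with two arms.
- The embedded bias baseline is taken at V2, after randomisation (Protocol, Study Procedures), so it precedes treatment but not allocation.
- Pre/post scores give up weekly ordering only relative to the weekly SPAI-B. LSAS-CA, SPAI, SSQ and ASSES are scheduled at V1 and V3 only (Protocol, Appendix I).
- Part of the SAP is in the past tense and gives a control group of 8. If results are already known, the analysis should be labelled post hoc.

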Appendix I. Table of Assessments

Assessment	Screening	V1	V3
Informed Assent/Consent	X		
Demographics	X		
Medical History Questionnaire and Screening	X		
Mini International Neuropsychiatric Interview for Children and Adolescents (MINI-KID)	X		
Social Phobia and Anxiety Inventory-Brief version	X		
Wechsler Abbreviated Scale of Intelligence (WASI-II)	X		
C-SSRS, Baseline	X		
Medications, Baseline	X		
Liebowitz Social Anxiety Scale for Children and Adolescents (LSAS-CA)		X	X
Social Phobia and Anxiety Inventory (SPAI)		X	X
Multidimensional Anxiety Scale for Children 2nd Edition (MASC-2)		X	X
Adolescent Social Self-Efficacy Scale (ASSES)		X	X
Social Skills Questionnaire (SSQ)		X	X
Medications, Since Last Visit		X	X
C-SSRS, Since Last Visit		X	X
Adverse Effects		X	X
Unanticipated Adverse Effects		As needed	
Study Exit		As needed	

Appendix II. Sample Debit Card Information
Attached separately.

Statistical Analysis Plan

WASABI: Wiring Adolescents with Social Anxiety Via Behavioral Interventions

Protocol Number: PSC-1016-19

NCT03990870

Document Date: July 8, 2019

(1) ANALYSIS POPULATIONS

There are three *a priori* defined analysis populations, including a primary analysis population (i), a secondary analysis population designed to compare effect sizes in populations with no missing data (ii) and a population who completed all training visits (iii)

- i. *Intent to Treat (ITT) population:* This is the *a priori* primary analysis population, defined as including all randomized participants who attended at least one group video call.
- ii. *Intent to Treat (ITT) Fully-Evaluable (FE) population:* This is a secondary analysis population, defined as including all members of the ITT population that complete a post-intervention visit. Note that a participant may complete a specific visit but have missing data for a test in which case the participant is in the overall FE population but does not contribute data to the FE population for that visit, e.g., the number of evaluable cases for a specific test on a specific visit may be smaller than the FE population for that visit because of missing data.
- iii. *Intent to Treat (ITT) Completers (C) population:* This is a secondary analysis population, defined as including all members of the ITT-FE population who complete all intervention sessions. Note that the C populations are strict subsets of the FE populations; a person who completes the target number of videocalls but does not complete the evaluation visit is not a member of the C population.

(2) STATISTICAL PLAN

Feasibility

The Phase I data analysis plan *a priori* defines a primary intent-to-treat (ITT) population, a set of secondary evaluation populations, a set of primary outcome measures, a set of secondary outcome measures, a set of potential mediators/moderators, a single primary evaluation time point, a criterion for statistical significance, and a statistical analysis methodology for secondary outcomes.

- The primary ITT population is defined as all participants who attend one dCBGT video call. Note that this includes all randomized participants except those who drop/withdraw post-randomization and pre-training.
- As the main goal of this Phase I trial is to evaluate the feasibility, acceptability and usability of the WASABI app. To this purpose, we will conduct an analysis of the following primary outcome measures in participants randomized to the WASABI+dCBGT arm:
 1. Assessment adherence (percentage of assessment sessions attended). Efforts will be made to assess all participants who have completed the minimum required intervention activities (attended at least 2 group calls, completed EMAs at least five times). *Based on our previous studies (CLIMB and MOODIFY) and pilot, we expect successful data collection of baseline and post-intervention outcome measures for ≥90% of participants.*
 2. Engagement with the digitally delivered Cognitive Behavioral Group Therapy (dCBGT) and with group Instant Messaging (IM): number of group sessions attended, number of messages sent per week on the group chat. *Based on our previous studies (CLIMB), we hypothesize that participants randomized to WASABI+ dCBGT will participate in 80% of the dCBGT sessions, and send at least 8 messages/week in the group chat.*
 3. EMA completion rate. *Based on our previous studies and pilot, we hypothesized that participants randomized to WASABI+ dCBGT would respond to 70% of the EMA prompts.*
 4. SPAI-B completion rate. *Based on our previous studies and pilot, we hypothesized that participants randomized to WASABI+ dCBGT would complete the weekly SPAI-B questionnaire 70% of the time.*

5. Overall program completion rate. *Based on findings from our previous findings (CLIMB) and from the pilot in anxious youth, we hypothesized full program completion in $\geq 79\%$ (≥ 8 of 12) study participants in the treatment arm.*

6. Usability ratings were obtained from all study participants post-intervention via a 7-point Likert-scale exit survey. This is a brief and embedded post-study questionnaire on program satisfaction, clarity, enjoyment, perceived benefits, and ease of fit into schedule. Participants rate each sentence on the following 7-point Likert scale: 1 = Completely Agree; 2 = Mostly Agree; 3 = Somewhat Agree; 4 = Undecided; 5 = Somewhat Disagree; 6 = Mostly Disagree; 7 = Completely Disagree. Clinical trials run by Posit Science software using this survey have shown high internal consistency with a Chronbach's alpha of .917. *Based on our previous findings, we hypothesize exit survey ratings of at least $\geq 4.5 \pm 1.5$ on the 7-point Likert scale items.*

7. Reported side effects (raw score). *Based on our previous findings, we expected 0 adverse events due to program use).*

The secondary outcome measures were collected by trained personnel blind to treatment assignment at baseline and after the intervention:

- clinician ratings of anxiety and social anxiety symptoms through the Liebowitz Social Anxiety Scale for Children and Adolescents (LSAS-CA)
- self-report inventories of social anxiety symptoms through the Social Phobia and Anxiety Inventory-Brief (SPAI-B) – at baseline, weekly during the intervention, and after the intervention;
- a broad measure anxiety and potential generalization of treatment to other anxiety domains, the Multidimensional Anxiety Scale for Children 2nd Edition (MASC-2);
- social skills by administering the Social Skills Questionnaire (SSQ) ;
- social functioning using the Adolescent Social Self-Efficacy Scale (ASSES).

The criterion for statistical significance is $p < 0.05$. Results with $p < 0.1$ will be described as trends.

The primary analysis time point is the post-intervention assessment.

For feasibility, we relied on descriptive statistics. For preliminary efficacy, in smaller sample sizes like ours, there is a greater likelihood that there will be larger differences at baseline between groups simply due to sampling error. Groups were compared on all baseline measures using Mann-Whitney U tests (for ordinal and continuous variables) or Pearson chi-square/Fisher's exact test (for categorical variables). To test whether groups differed in change over time, data were analyzed via linear mixed-effects models. Mixed-effects models are ideal for the analysis of longitudinal data, due to the fact that it tolerates missing observations—assuming that it is missing at random (MAR). First, simple growth models (change from baseline to post) were conducted to examine change over time (for all participants). Because complete case analyses have been shown to provide biased estimates in the presence of missing data (Enders, 2010), data were then modeled using the intent-to-treat (ITT) framework, in which all randomized subjects are included in the analysis, and missing data were handled via Full Information Maximum Likelihood (FIML). This method for handling missing data is considered a gold standard approach, as it gives relatively unbiased estimates (Enders, 2010), and is the standard for the analysis of randomized trials. For all models, fixed effects of time, group, and group x time interaction were included; a random intercept of subject was used. Kenward-Roger degrees of freedom were used due to the small sample size; statistical significance was evaluated at a two-sided alpha of $p = 0.05$; however, null hypothesis testing was de-emphasized given the small sample size of the control group ($n = 8$). We emphasize the effect size (Cohen's d) instead. Although various estimates of effect size exist for LMM, we chose a simplified version, defined as:

$$\frac{(\Delta_{(dCBT+WASABI)} - \Delta_{(dCBT)})}{\sigma_{pre}}$$

Where Δ refers to slope (i.e., change from baseline to post-intervention) and σ_{pre} refers to the pooled baseline standard deviation. Thus, values of d refer to change in standard deviation units from baseline.
